WEEK ^b	to -1				1							2	2 c							3			4
DAY																							
HOUR (relative to infusion) ^d		Pre 757	EOI 757	2	6	24	48	96	Pre 404	EOI 404	Pre 757	EOI 757	2	6	24	48	Pre 757	EOI 757	2	6	24	48	168
Other Assessments																							
MRI Brain ^x	Х																						
Radiological imaging and tumor burden assessment ^y	х																						
			•		•		•							•		•			•		•	Pa	ge 3 of

Protocol Number: 20200439

Date: 05 June 2024 Page 169 of 176

Table 11-7. Schedule of Activities: One-Step Dosing – Cycle 1 Only (AMG 404 Administered

STUDY PERIOD/ TREATMENT CYCLE	SCR ^a											Су	cle 1	only									
WEEK ^b	-3 to -1				1						2	ıc							3				4
DAYb																							
HOUR (relative to infusion) ^d		Pre 757	EOI 757	2	6	24	48	96	Pre 757	EOI 757	2	6	24	48	Pre 404	EOI 404	Pre 757	EOI 757	2	6	24	48	168
General/Safety Assessm			1																				
Informed consent	X																						
Clinical Evaluatione	Х	Χ			L	Χ	Χ	Χ	Χ			L	Χ	Χ	Χ					 	X	Х	Х
Vital signs, pulse oxf	X	Χ	Х		X ^f		Χ	Х	Χ	Χ		X ^f		Χ	Χ	Χ	Χ	X		X ^f	•	Х	X
12-lead ECG ^g	X	Χ	Χ							Χ								Х					
ECHO or MUGA	X																						
Adverse event review			← ==	=====		-====		=====		====	====	====	=====	=====		=====		=====	=====	=====		=====	===→
Serious adverse event review	← =====	====	=====	=====	=====	=====	====		=====					====	=====	=====	====	=====	=====	======	=====	======	===→
Prior/concomitant medication																===→							
Local Laboratory Assess	ments																						
CBC with differential	X	Х				Х	Х	X	Х				Х	Х	Х						X	X	X
Coagulation	Х	Χ				Х		Х	Х				Х		Х						Х		
Chemistry panelh	Х	Х			Х	Х	Х	Х	Х				Х	Х	Х						Х	Х	Х
Lipase and Amylase	X	Х																					
Urinalysis	Х																						
Serum/urine pregnancy Test ⁱ	X	Х																					
Safety endocrine paneli	Х																						
CRP		Χ			Х	Х	Χ		Χ			Χ	Χ	Χ	Χ					Х	Х	Х	Х
Ferritin		Χ			Х	Х	Χ		Χ			Χ	Х	Χ	Χ					Х	Х	Х	Х
HBsAg, HBcAb, HCV Ab, HIV	Х																						
Central and Biomarker L	aboratory To	ests																					

Page 1 of 2

Protocol Number: 20200439

Date: 05 June 2024 Page 170 of 176

Table 11-7. Schedule of Activities: One-Step Dosing – Cycle 1 Only (AMG 404 Administered Day 15)

															`								
STUDY PERIOD/ TREATMENT CYCLE	SCR ^a											Су	cle 1 c	only									
																			3				
WEEK ^b	-3 to -1				1						2	C											4
DAY ^b																							
HOUR (relative to infusion) ^d		Pre 757	EOI 757	2	6	24	48	96	Pre 757	EOI 757	2	6	24	48	Pre 404	EOI 404	Pre 757	EOI 757	2	6	24	48	168
Central and Biomarker L	aboratory T	ests (d	continu	ıed)																			
Study Drug Administration	on																						
Tarlatamab IV infusion ^t																							
AMG 404 IV infusion ^t Dexamethasone or		Х							Х								Х						
equivalentu		^															^						
IV Hydration ^v		_	Χ						_	Х					_			Χ					
Hospital stay ^w		+=	====	=====	=====	==→			←==	=====	=====	=====	==→		←==	====	====		=====	=====	===→		
Other Assessments MRI Brain ^x				1		ı	ı	ı				ı								1			
Radiological imaging and tumor burden assessment ^y	X																						
Factoria de suite de f			1	1	1	I	I	I	ı	1	1	I			ı				1	 	1	Page	2 of 2

Protocol Number: 20200439

Date: 05 June 2024 Page 171 of 176

Table 11-8. Schedule of Activities: Cycle 2 and Beyond (If AMG 404 was Administered on or 8 in Cycle 1)

STUDY PERIOD/ TREATMENT CYCLE	TREATMENT CYCLE WEEKb DAYb HOUR (relative to infusion)d 44 General/Safety Assessments Clinical Evaluatione X Vital signs, pulse oxf X 12-lead ECGg ECHO or MUGA Adverse event review	X X	X							Pre 7.	EOI					4	Q cy		Q2 cyc 1	EOThh	SFU-1 ^{ee}	SFU-2 ^{ff}	LTFU ^{aa}
## HOUR (relative to infusion) ^d ## ## ## ## ## ## ## ## ## ## ## ## ##	HOUR (relative to infusion)d 4 4 4 4 4 4 4 4 4 4 4 4 4 4 4 4 4 4 4	X X	X				48	96		Pre 7	EOI					4	1	3	1				
HOUR (relative to infusion)d	HOUR (relative to infusion)d General/Safety Assessments Clinical Evaluations X Vital signs, pulse oxf X 12-lead ECGg ECHO or MUGA Adverse event review	X X	X	N			48	96		Pre 7	EOI :					•							
Ceneral/Safety Assessments	General/Safety Assessments Clinical Evaluation® X Vital signs, pulse oxf X 12-lead ECG® ECHO or MUGA Adverse event review	X X	X	2			48	96	168	Pre 7	EOI :												
Clinical Evaluation® X	Clinical Evaluation ^e X Vital signs, pulse ox ^f X 12-lead ECG ^g ECHO or MUGA Adverse event review									57	757	2	6	24	48	168							
Vital signs, pulse ox'	Vital signs, pulse oxf X 12-lead ECG ^g ECHO or MUGA Adverse event review																						
12-lead ECGg	12-lead ECG ^g ECHO or MUGA Adverse event review					X	Х	Х	Х	Х				Х	Х	Х	Χ	Х		Х	Х	X	
12-lead ECGg	12-lead ECG ^g ECHO or MUGA Adverse event review	4			Χ ^τ		Х	Х	Х	Х	Χ	u u	X ^f		Χ	Χ	Χ	Х		Х	Х	X	
ECHO or MUGA Adverse event review Serious adverse event review Prior/concomitant medication Local Laboratory Assessments CBC with differential X X X X X X X X X X X X X X X X X X X	Adverse event review	4									Χ												
Adverse event review Serious adverse event review Prior/concomitant medication Local Laboratory Assessments CBC with differential X X X X X X X X X X X X X X X X X X X	Adverse event review	4																					
Serious adverse event review			=====	=====	=====	=====	=====	=====	=====	=====	====	=====	=====	=====	====	====	=====	=====	=====	=====	====	=→	
Prior/concomitant medication	20	`				=====	=====	=====		====		=====	====				=====	=====	=====	=====	====		=
Prior/concomitant medication	review																						-
CBC with differential X	Prior/concomitant	======				=====	=====				=====	=====	====			====	=====	=====	=====	=====	====		= →
CBC with differential X	Local Laboratory Assessments																						
Chemistry panel ^h X X	CBC with differential X					Х	Х		Х	Χ				Х	Χ	Χ	Х	Х		Х	Х	Х	
Chemistry panel ^h X X	Coagulation X					Х				Х				Х			Χ			Χ	Χ	Х	
Lipase and Amylase X X X Urinalysis X X X Serum/urine pregnancy Testi X X X Safety endocrine paneli X X X X CRP X X X X X X X Ferritin X X X X X X X X X X					Х	Х	Х	Х	Х	Х				Х	Χ	Χ	Χ	Х		Х	Х	Х	
Serum/urine pregnancy X																					Χ		
Serum/urine pregnancy X	Urinalysis																		Х				
CRP X	Serum/urine pregnancy																Х				Х	Х	
CRP X	Safety endocrine panel ^j X																Χ			Х	Х		
Ferritin X<					Х	Х	Х		Χ	Χ			Χ	Χ	Χ	Χ	Х				Х		
					Х	Х	Х		Χ				Χ			Χ				Х			
	Central and Biomarker Laboratory	Tests	•																		•		

Page 1 of 2

Product: Tarlatamab (AMG 757), AMG 404 **Protocol Number:** 20200439

Page 172 of 176 Date: 05 June 2024

Table 11-8.	Sc	hedu	ule of	Acti	vities	s: Cy	ycle 2	and	Веу	ond	(If A	MG	404 v	was	Adm	inis	tere	d on			in Cy	cle 1)	
STUDY PERIOD/ TREATMENT CYCLE								Су	cle 2									Qc	ycbb	Q2 сус	EOThh	SFU-1ee	SFU-2ff	LTFUaa
WEEK ^b					1					2°			3				4	1	3	1				
DAYb																	-			-				
HOUR (relative to infusion) ^d	Pre 404	EOI 404	Pre 757	EOI 757	2	6	24	48	96	168	Pre 757	EOI 757	2	6	24	48	168							
General/Satety Assessme	nts																							
Tarlatamab PK collection ^p			Х	Х		X	Х	Х		Х	Х	Х		Х	Х	Х	Х	Xq						
AMG 404 PK collection ^p	Χ	Χ									Χ							Xr					Χ	
Study Drug Administration Tarlatamab IV infusion ^t AMG 404 IV infusion ^t Hospital stay ^w							==+				- =				== ->									
Other Assessments										ı						I		l	ı					
MRI Brain ^x																								
Radiological imaging and tumor burden assessment ^y																				Х	X ^z	X ^z		X ^{dd}
Survival Status and subsequent cancer therapy ^{aa}																								Х
																							Page:	2 of 2

Protocol Number: 20200439

Date: 05 June 2024 Page 173 of 176

Table 11-9. Schedule of Activities: Cycle 2 and Beyond (If AMG 404 was Administered on in Cycle 1) SFU-1® SFU-2ff Q2 cyc LTFU^{aa} EOThh STUDY PERIOD/ Q cycbb TREATMENT CYCLE Cycle 2 WEEK^b 2° DAYb EO Pre 404 **EOI 404** Pre EO **HOUR** (relative to 168 96 24 24 **48 48** N တ 6 168 757 infusion)d 757 757 General/Safety Assessments Clinical Evaluation^e Χ Χ Χ Χ Х Х Х Vital signs, pulse oxf Χ Χ Xf Χ Χ Χ Χ Χ Х Χ Xf Χ Χ Χ Χ Χ Х Χ 12-lead ECG^g Х Χ X^{cc} X^{cc} ECHO or MUGA Adverse event review Serious adverse event review Prior/concomitant medication Local Laboratory Assessments CBC with differential Х Х Х Χ Χ Х Х Χ Х Χ Coagulation Χ Х Χ Χ Χ Χ Х Χ Chemistry panelh Χ Χ Х Х Χ Χ Χ Χ Χ Χ Lipase and Amylase Х Χ Χ Urinalysis Χ Serum/urine pregnancy Χ Х Χ Testⁱ Safety endocrine panel Х Χ Χ Х CRP Х Χ Х Χ Х Χ Χ Х Χ Χ Х Ferritin Χ Χ Χ Х Χ Χ Χ Central and Biomarker Laboratory Tests

Page 1 of 2

Protocol Number: 20200439

Date: 05 June 2024 Page 174 of 176

0 6	· obo	dula a	£ A a	41.,141	001	Cyclo	2 01	d Da		۲ /۱۴	A N// C	2 404	Lwa	- A d	min	oto	10d 0	_				1/4	OT 1
.y. c	cne	dule c	oi AC	uviu	es. (Cycle	Zan	iu be	yon	a (II	AIVIC	3 4 04	wa	s Au	111111	ISte	rea oi	1	11	Cyc	le 1)		
							0	ala O									Qc	yc ^{bb}	Q2 cyc	EOThh	SFU-1®	SFU-2ff	LTFUªª
			1				Cy	CIE 2			2					1	1	3	1				
																-		J					
Pre 757	EOI 757	2	6	24	48	96	168	Pre 404	EOI 404	Pre 757	EOI 757	2	6	24	48	168							
Х	Х		Х	Х	Х		Х			Х	Х		Х	X	Х	Х	Xq						
								Χ	Χ									Xr				Χ	
1																							
← =	====	=====	====	== →				←==	====	====	====	====	====	= →									
	1				1	ı	ı		1	ı			1										
																			Х	Xz	Xz		Xd
																							Х
			Carlota	mah	ie infu	sad. Di	∩т⊔ _	adrar	ooort													Page	20
	Pre 757 ×	Pre 757 X	EOI 757 X	1 6 X X X X X	1 6 X X X Pre 757 X X X X	1 6 X X X Pre 757 X X X X X	1 24 48 Pre 757 X X X X X X X X X X X X X X X X X X	Cy 1 2° 48 96 168 Pre 757 X X X X X X	Cycle 2 1 2° Pre 404 Pre 757 X X X X X X X X	Cycle 2 1 2° Pre 757 REOI 757 X X X X X X X X X X X X X X X X X X X	Cycle 2 1 2° Pre 757 EOI 404 Pre 757 X X X X X X X X X X X X X X X X X X X	Cycle 2 1	Cycle 2 1 2° 3 Pre 757 Pre 757 2 6 24 48 96 168 404	Cycle 2 1 2° 3 Pre HOI 757 E OI 757 X X X X X X X X X X X X X X X X X X X	Cycle 2 1 2° 3 Pre 757 2 6 24 48 96 168 Pre 404 404 X X X X X X X X X X X X X X X X	Cycle 2 1 2° 3 Pre 757 2 6 24 48 96 88 440 404 757 757 2 6 24 48 X X X X X X X X X X X X X X X X X X X	Cycle 2 1	Cycle 2 1 2° 3 4 1 Pre 757 2 6 24 48 96 168 Pre 404 40 757 757 2 6 24 48 168 X X X X X X X X X X X X X X X X X X X	Tree For 757 2 6 24 48 96 16 88 44 4 1 3 3 2 6 24 48 16 8 4 4 1 3 3 4 4 1 3 3 4 4 1 3 3 4 4 1 1 3 3 4 4 1 1 3 3 4 4 1 1 3 3 4 4 1 1 3 3 4 4 1 1 3 3 4 4 1 1 3 3 4 4 1 1 3 3 4 4 1 1 3 3 4 1 1 1 1	Cycle 2 1 2° 3 4 1 3 1 Pre TO 757 2 6 24 48 96 8 8 44 44 44 47 77 77 77 2 6 24 48 8 8 8 8 8 8 8 8 8 8 8 8 8 8 8 8 8	9. Schedule of Activities: Cycle 2 and Beyond (If AMG 404 was Administered on	9. Schedule of Activities: Cycle 2 and Beyond (If AMG 404 was Administered on in Cycle 1) Q cycle 2	Cycle 2 1 2° 3 4 1 3 1 Pro 757 2 6 24 48 96 68 404 404 757 757 2 6 2 48 168

c See Section 6.2.1.3 for more details regarding Step Dosing.

AMGEN

[•] End of infusion (EOI) assessments or procedures are to be completed immediately after infusion of tarlatamab. EOI indicates the time when the investigational product infusion and saline flush is completed. Assessments after EOI indicate the time relative to EOI. Investigational product infusions are marked in the EOI column.

Protocol Number: 20200439

Date: 05 June 2024 Page 175 of 176

- Assessments are done pre-infusion unless specified. Laboratory assessments that were done within 24 hours prior to infusion do not need to be repeated (except for cycle 1 dosing where laboratory assessments that were done within 48 hours prior to infusion do not need to be repeated). All assessments and procedures should be collected at the exact nominal time point as noted in the Schedule of Assessments. If unable to perform a procedure at the specified nominal time point, collect it as close as possible to the nominal time point and record the actual collection time. Clinical evaluation including physical exam, ECOG, weight and neurological exams, writing test, and mini-mental status exams (neurology specialty consultation service as clinically indicated). Mini mental status exams and writing test are required on clinical evaluation required per dosing regimen),) in cycle 1. Mini mental status exam and writing test may be performed in (may be performed if clinically indicated on cycle 2 and beyond at the investigator's discretion. Performed at screening only: demographics, medical history, and height. Clinical evaluation should be completed within 6 hours prior to the first dose of tarlatamab. Vital signs (BP, HR, RR, temp) and pulse oximetry will be assessed. Vitals will be taken pre-AMG 404 infusion and at AMG 404 EOI. For each tarlatamab-infusion for the first 2 cycles (during the hospitalization period) vital signs should be assessed as detailed in Section 8.4.1. ECGs will be collected once and considered safety ECGs. ECGs should be collected prior to blood draws when assessments are conducted at the same nominal time point (pre-infusion timepoints for tarlatamab and AMG 404 may be collected 15 minutes prior to infusion, post-infusion time points for tarlatamab may be collected ± 15 minutes of indicated time point). See Section 8.4.5. For cycles 1 and 2 only, please collect LDH, phosphorus, and uric acid along with the chemistry panel for TLS monitoring. Serum pregnancy test at screening; serum or urine pregnancy test monthly until from the last investigational product (tarlatamab or AMG 404) dose. Additionally, a pregnancy test at after last dose of AMG 404. Safety endocrine panels: ACTH, cortisol, TSH, and FT4 will be evaluated at screening, of every cycle starting with cycle 2, EOT, and SFU-1. Prolactin, FSH, LH, testosterone (in males) and estradiol (in females) will be evaluated only at screening, EOT, and as clinically indicated. m A tumor biopsy is required at screening if patient has received any treatment prior to participating into this study and biopsy can be performed safely as determined by the investigators. Tumor tissue (archival or fresh biopsy) must be available. Subjects must consent to allow the acquisition of FFPE material (block or unstained slides) by study personnel.
- q For cycles 3 and 4, collect tarlatamab PK samples at pre- and post-infusion. For all remaining cycles beginning with cycle 5, collect at pre-infusion only. tarlatamab PK samples to be collected until end of cycle 12 only
- r AMG 404 PK samples to be collected at pre-infusion and end of infusion in cycles 3, 5, 7, 9, and 11 and at pre-infusion in cycles 4, 6, 8, 10, and 12.

Protocol Number: 20200439

Date: 05 June 2024 Page 176 of 176

u	Dexamethasone mg IV (or equivalent dose of other corticosteroids) will be administered within 1 hour prior to all tarlatamab doses, in week 1 and step doses of tarlatamab in cycle 1 only.
٧	Refer to Section 6.1.4 for administration details.
Х	All subjects must have MRI/CT of the brain performed within 21 days prior to the first dose of tarlatamab. All brain scans on protocol are required to be MRI unless MRI is contraindicated, then CT with contrast is acceptable. Subsequently, MRI brain can be performed at any time if clinically indicated per standard of care.
у	
	Tumor burden assessments will be performed based on modified RECIST 1.1 guidelines (see Section 11.9).
aa	LTFU will be conducted every 3 months (± 2 weeks) for 1 year from the first dose of tarlatamab on all subjects who have not withdrawn consent by clinic visit, telephone, or chart review to assess for survival and/or the commencement of subsequent cancer therapy only. If the investigator becomes aware of serious adverse events suspected to be related to investigational product or any fatal adverse event (regardless of causality) after the protocol-required reporting period (as defined in Section 8.4.9.1.3) is complete, then these serious adverse events will be reported to Amgen immediately and no later than 24 hours following the investigator's awareness of the event on the Event eCRF.
bb	Assessments to be completed at specified timepoint beginning with cycle 3 and at each subsequent cycle unless otherwise specified.
СС	For cycles 3 and 4 only: please collect ECG post-tarlatamab infusion. No further ECG's are collected after cycle 4.

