- Other examples of non-measurable lesions include:
 - Lesions with prior local treatment:
 - Tumor lesions situated in a previously irradiated area, or an area subject to other loco-regional therapy, should not be considered measurable unless there has been demonstrated progression in the lesion.
 - Biopsied lesions
 - Categorically, clusters of small lesions, bone lesions, inflammatory breast disease, and leptomeningeal disease are non-measurable. See Imaging Procedural Manual provided by the central imaging core laboratory for additional guidance.

Protocol Number: 20200439

Date: 05 June 2024 Page 159 of 176

Index lesions and measurable tumor burden:

Index lesions:

- Measurable lesions (≤ 5 lesions per organ, ≤ 10 total) selected at baseline on the basis of
 - Size and suitability for accurate repeated measurements by imaging.
 - Representative of the subject's tumor burden, all organs involved and overall disease status

Non-index lesions:

- All measurable lesions not selected as index lesions and non-measurable lesions
- Non-index lesions will be qualitatively evaluated
 - Values: 'Present', 'absent' or 'unequivocal progression'.
- Other definitions
 - Unable to evaluate (UE): Any lesion present at baseline which was not assessed or was unable to be evaluated leading to an inability to determine the status of that particular tumor for that time point
 - Not Available (NA): Scan not available
 - Not Done (ND): Radiologic imaging was not performed at this time point to evaluate the index lesions

Index lesion response:

- At baseline and all subsequent tumor assessments, measurable tumor burden is the sum of the longest diameters (SLD) of all index lesions
- Complete Response (CR) disappearance of all measurable lesions
 - Pathologic lymph nodes must have reduction in short axis to < 10 mm
- Partial Response (PR) decrease of 30% or greater in tumor burden compared with baseline
- Stable Disease (SD) not meeting the criteria for CR, PR, or progressive disease
- Progressive Disease increase of 20% or greater in tumor burden compared with nadir, or the appearance of one or more new lesions

Non-index lesion response:

- CR disappearance of all non-index lesions
 - Pathologic lymph nodes must have reduction in short axis to < 10 mm
- SD persistence of one or more non-index lesions, not meeting the criteria for CR or progressive disease

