- Progressive disease unequivocal progression of existing non-index lesions, or the appearance of one or more new lesions

Protocol Number: 20200439

Date: 05 June 2024 Page 160 of 176

Overall response:

CR

- Complete disappearance of all lesions
 - Pathologic lymph nodes must have reduction in short axis to
 10 mm
- Confirmation scan required repeat, consecutive assessment no less than 4 weeks from the date of the first documented response
- o CR is dated at time of confirmation scan
- PR
- Decrease in tumor burden ≥ 30% relative to baseline, or
- Complete disappearance of all index lesions with presence of non-index lesions
- Confirmation scan required repeat, consecutive assessment no less than 4 weeks from the date of the first documented response
- o PR is dated at time of confirmation scan
- SD
- o Index lesions not meeting criteria for CR, PR or progressive disease, or
- In subjects with only non-index disease, persistence of one or more non-index lesions
- Progressive Disease
 - Radiologic detection of ≥ 20% increase in tumor burden relative to nadir and at least 5 mm absolute increase, or
 - Unequivocal progression of non-index lesions, or
 - The presence of new lesions
 - Confirmation scan required repeat, consecutive assessment from the date of the first documented response
 - Radiographic progressive disease is confirmed at repeat imaging

it:

- Tumor burden remains increased by ≥ 20% and at least
 5 mm absolute increase relative to nadir, or
- Unequivocal progression of non-index lesions is observed, or
- New lesions are present
- Subjects with a global deterioration of health status requiring discontinuation of treatment prior to radiologic confirmation of disease progression should have the reason for treatment discontinuation classified as 'clinical disease progression' not 'radiographic progressive disease'. Every effort should be made to radiologically confirm progression even after discontinuation of treatment.

Protocol Number: 20200439

Date: 05 June 2024 Page 161 of 176

Summary of Measure	men	t and Tumor Respo RECIST 1.		ent Based on Modified									
Measurable lesions		 Non-nodal lesion measurement) Pathologic lympi ≥ 15 mm 		nidimensional est diameter short axis									
Measurement of each lesion		Non-nodal lesion planePathologic lymp	_	t diameter (mm) in the axial axis (mm)									
Tumor burden		Sum of the longUp to 5 lesions p	•	SLD) of all index lesions o 10 total									

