Response assessment: index lesions (calculated from % chan in tumor burden)	ge	 CR: Disappearance of all lesions Pathologic lymph nodes short axis < 10 mm PR: ≥ 30% decrease from baseline SD: Does not meet criteria for CR, PR or progressive disease. Progressive disease: ≥ 20% increase (and ≥ 5 mm absolute increase) from nadir 											
Response assessment: non-index lesions		 CR: Disappearance of all lesions Pathologic lymph nodes short axis < 10 mm SD: Persistence of one or more non-index lesion(s) Progressive disease: Unequivocal progression of existing non-index lesions 											
New Lesions		The presence of new lesion(s) defines progression											
Confirmation		Confirmation by su required for CR, P	•	essment after ≥4 weeks ssive disease.									
Summary of N	Modi	fied RECIST 1.1 Ov	erall Respons	e Assessment									
Index lesions (tumor burden) ^a , %	No	n-Index lesions	New lesions	Overall Response using modified RECIST 1.1									
↓ 100%	Ab	sent	Absent	CR ^b									
Noned	Ab	sent	Absent	CR⁵									
↓ 100%	Pre	esent	Absent	PR^b									
↓≥30 %	Ab	sent/Present	Absent	PR^{b}									
↓ < 30% to ↑ < 20%	Ab	sent/Present	Absent	SD									
Noned	Pre	esent	Absent	SD									
↑≥ 20%	An	У	Any	Progressive disease ^c									
Any		equivocal gression	Any	Progressive disease ^c									
Any	An	y	Present	Progressive disease ^c									
NA/ND/UE	Ab	sent/Present	Absent	UE									
Noned	NA	/ND/UE	ND/UE Absent										

CR = complete response; NA = not available; ND = not done; PR = partial response; RECIST = Response Evaluation Criteria in Solid Tumors; **SD = stable disease;** UE = unable to evaluate

^a Decrease assessed relative to baseline. Increase assessed relative to nadir.

^b Response: CR and PR require a confirmation assessment after ≥ 4 weeks, may also wait until the next scheduled imaging

^c Progression: Progressive disease requires a confirmation assessment

^d Subjects with non-index lesions only

Protocol Number: 20200439

Date: 05 June 2024 Page 162 of 176

11.10 Appendix 10. Schedule of Activities:

Table 11-4. List of Schedule of Activities Tables

Quick link to Schedule of Activities	Table Title
Table 11-5	One-Step Dosing – Cycle 1 only (AMG 404 Administered
Table 11-6	One-Step Dosing – Cycle 1 only (AMG 404 Administered
Table 11-7	One-Step Dosing – Cycle 1 only (AMG 404 Administered
Table 11-8	Cycle 2 and Beyond (AMG 404 Administered on in Cycle 1)
Table 11-9	Cycle 2 and Beyond (AMG 404 Administered on in Cycle 1)

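### Protocol Appendix 9 defines index-lesion progression both with and without a 5 mm minimum, so a small rise from a nadir sum below 25 mm can be coded PD or not PD

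*Protocol*

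**What the plan says.** All the response rules are in Protocol Section 11.9 (Appendix 9).

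**PD on index lesions**
- Index-lesion response bullet: "increase of 20% or greater in tumor burden compared with nadir, or the appearance of one or more new lesions". There is no millimetre condition.
- Overall-response grid: PD for a rise of 20% or more. Neither the row nor its footnotes give a millimetre condition. The SD row stops at a rise below 20%.
- Overall-response text: "Radiologic detection of ≥ 20% increase in tumor burden relative to nadir and at least 5 mm absolute increase". The rule for confirming PD on the repeat scan carries the same 5 mm minimum.
- Measurement summary, index-lesion row: "≥ 20% increase (and ≥ 5 mm absolute increase) from nadir".
- SD in the overall-response text is the default category: "Index lesions not meeting criteria for CR, PR or progressive disease".

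**CR with nodal index lesions**
- Index-lesion text: "Pathologic lymph nodes must have reduction in short axis to < 10 mm". The measurement summary agrees: "Pathologic lymph nodes short axis < 10 mm".
- Overall-response grid: for subjects with index lesions, CR only at a 100% fall in tumor burden. Any other fall of at least 30% is PR.

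**SAP.** Appendix B derives BOR from the time-point responses. It waives confirmation of PD when that PD is the last evaluable assessment. Table 10 in Appendix C dates a PFS event at the first sighting of PD. DOR follows the same censoring strategy (Section 5).

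**The concern.** The appendix does not say which statement governs. An assessor working from the grid and one working from the overall-response text can give different codes to the same measurements. The SAP takes those codes as its input and has no step that recomputes response from lesion measurements.

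The subjects exposed are those with a small nadir sum, and good responders are likely to be among them. For such a subject a change of a few millimetres, below the appendix's own minimum, could be recorded as progression. ORR, DCR, DOR and PFS are secondary endpoints in an open-label multicenter study, so the rule should be the same for everyone.

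**Working it through.** No planned figure such as sample size, power or event count depends on this point, so there is nothing to reproduce. The check applies each written rule to the same measurements.

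**Where the PD rules part.** Rule A is a rise of at least 20% over nadir. Rule B is a rise of at least 20% and at least 5 mm. They can differ only if 0.20 × nadir < 5 mm, that is nadir < 5 / 0.20 = 25 mm.

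| Baseline / nadir / current sum (mm) | Rise over nadir | Change from baseline | Rule A | Rule B |
|---|---|---|---|---|
| 25 / 20 / 24 | +4 mm, +20% | −4% | PD | SD |
| 12 / 10 / 12 | +2 mm, +20% | 0% | PD | SD |
| 28 / 24 / 28.9 | +4.9 mm, +20.4% | +3.2% | PD | SD |
| 40 / 20 / 24 | +4 mm, +20% | −40% | PD | PR |
| 30 / 25 / 30 | +5 mm, +20% | 0% | PD | PD |
| 60 / 50 / 60 | +10 mm, +20% | 0% | PD | PD |

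The fourth row is the responder. The sum is still at least 30% below baseline, so the alternative to PD is PR, not SD.

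**How a sub-5 mm call gets through the SAP**
1. *PD at the last evaluable assessment.* Confirmation is waived, so Rule A gives a PFS event at that scan. Under Rule B, with no death recorded, the subject is censored there.
2. *PD confirmed later.* Take nadir 20 mm, then 24 mm, then 26 mm (+6 mm, +30%). Rule A dates progression at the 24 mm scan and Rule B at the 26 mm scan. The gap is at least the 4-week confirmation interval: 28 × 12 / 365.25 = 0.92 months. It is 56 × 12 / 365.25 = 1.84 months at the 8-week scan interval in the footnote to SAP Table 8. For a responder, DOR shortens by the same amount.
3. *BOR and DCR.* Suppose baseline is itself the nadir (20 mm) and the first post-baseline scan, also the last evaluable one, reads 24 mm. Rule A gives BOR of PD (Table 8, row C33). Rule B gives SD (row C24) if the scan meets the minimum time for SD, and the subject then counts toward DCR.
4. *BOR after a first PR.* If the 24 mm reading falls on the scan due to confirm the PR, Table 8 gives SD for PR followed by PD (row C15) and PR for PR followed by PR (row C12).

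**CR with nodal index lesions** (nodes by short axis)
- One node, 15 to 9 mm: 1 − 9/15 = 40% fall.
- One node, 20 to 9 mm: 1 − 9/20 = 55% fall.
- Lesion 30 to 0 mm plus node 18 to 9 mm: 1 − 9/48 = 81.2% fall.

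With all other disease gone, each is CR by the text and PR by the grid. An index node starts at 15 mm or more, so normalising below 10 mm is a fall of more than 1 − 10/15 = 33.3%. The grid result is therefore always PR, never SD.

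**The case against.** **The 5 mm rule may already govern.** Three statements carry it: the overall-response definition, the confirmation rule and the index-lesion summary row. The grid is a summary with a percentage column, and its footnote requires PD to be confirmed. A rise of 3 mm cannot be confirmed on tumor burden alone. This stands as a limit: many sub-5 mm calls should not survive a repeat scan. It is not a cure, because of the waiver at the last evaluable assessment and the dating at first sighting.

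**Other documents or readers may settle it.** The appendix refers to an imaging manual from a central imaging core laboratory, and SAP Appendix B also derives BOR by central review. The manual is not among the documents, so it may resolve the point. The protocol itself does not.

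**The CR row may be shorthand.** A 100% fall can be read as disappearance, which the text defines to allow small nodes. That is a fair reading, but nothing sets a normalised node to zero in the sum. In any case ORR and DCR count CR and PR alike, so neither changes.

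**A stronger reading to avoid.** The appendix says that "measurable tumor burden is the sum of the longest diameters (SLD) of all index lesions". A reader might infer that nodes enter by their long axis and that ORR can shift for this reason. For example, take a lung mass 40 to 32 mm plus a node 30 × 20 to 24 × 9 mm. Longest diameters give (32 + 24)/(40 + 30), a 20.0% fall (SD). The nodal short axis gives (32 + 9)/(40 + 20), a 31.7% fall (PR). The documents do not support this. The appendix defines nodal size as the diameter perpendicular to the long axis, and its measurement row, though damaged in the PDF text, treats nodes separately by axis. Sites are not told to record a nodal long axis. The label for the sum is loose, but the ORR claim does not follow.

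**Conclusion.** The PD definition is inconsistent and should be reconciled. The conflict is confined to nadir sums below 25 mm and rises of at least 20% but under 5 mm. Within that band the same scan is PD or not PD, and the alternative is SD or PR depending on the distance from baseline. PFS, DOR, BOR and possibly DCR can be affected. For an affected subject the change is an event in place of censoring, or a progression date earlier by one scan interval (0.92 to 1.84 months in the example).

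The nodal CR conflict is secondary and alters only the split between CR and PR.

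This rests on three assumptions: that time-point codes enter the SAP derivation as recorded, that the nadir may be the baseline value, and that the imaging manual does not already impose one rule. The documents give no basis for counting the subjects affected. No hypothesis is tested and these endpoints are descriptive, so this is a matter to correct before analysis, not a threat to the trial's primary purpose.

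**What to change.** In the SAP (Section 5 and Appendices B and C):
- State one rule set. PD on index lesions needs at least 20% and at least 5 mm over nadir, as in the protocol's overall-response text. CR allows index nodes below 10 mm short axis. Nodes enter the sum by short axis.
- Derive the time-point index response from the recorded lesion measurements under these rules, and query every call that disagrees.
- Record the clarification in SAP Section 10, which now reports no changes.

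In Protocol Appendix 9, add the 5 mm minimum to the index-lesion PD bullet and the grid's PD row. Let the SD row take smaller rises, subject to the PR criterion. Adjust the grid's CR row and the adjoining PR rows for normalised nodes.

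The SAP step matters more. Enrollment ended in January 2023, and rewording the appendix will not recode scans already read. The cost is a programmed check on lesion data that should already be held, since the SAP plans to summarize baseline sums of diameters. No new scans are needed, and a few time-point responses may change.
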